7.4.2 Treatment Labels

In general, the results will be presented by treatment location (face/chest or scalp) and treatment group within treatment location as well as overall by treatment group (ingenol disoxate versus vehicle). The following treatment labels will be used: 0.018%, 0.037%, Ingenol disoxate and Vehicle.

Trial ID: LP0084-1369	Date: 27-May-2018	Version: 1.0 Page 11 of 14
-----------------------	-------------------	-------------------------------

Appendix I

Tables

- Analysis of time to first SCC in the treatment area from Visit 2 in trials LP0084-1193, -1194, -1195 and -1196: full analysis set
- Analysis of time to first SCC or other skin neoplasia in the treatment area from Visit 2 in trials LP0084-1193, -1194, -1195 and -1196: full analysis set
- Analysis of time to first SCC in the treatment area from Visit 7 in trials LP0084-1193, -1194, -1195 and -1196: full analysis set
- Analysis of time to first SCC or other skin neoplasia in the treatment area from Visit 7 in trials LP0084-1193, -1194, -1195 and -1196: full analysis set
- Incidence of SCC in the treatment area from Visit 2 in trials LP0084-1193, -1194, -1195 and -1196: full analysis set
- Incidence of SCC or other skin neoplasia in the treatment area from Visit 2 in trials LP0084-1193, -1194, -1195 and -1196: full analysis set
- Incidence of SCC in the treatment area from Visit 7 in trials LP0084-1193, -1194, -1195 and -1196: full analysis set
- Incidence of SCC or other skin neoplasia in the treatment area from Visit 7 in trials LP0084-1193, -1194, -1195 and -1196: full analysis set
- Demographics: full analysis set
- Demographics: subjects enrolled in LP0084-1369
- Disposition: full analysis set
- Disposition: subjects enrolled in LP0084-1369
- Concomitant medication in LP0084-1369: subjects enrolled in LP0084-1369
- Scarring, shift table by visit (observed cases): safety analysis set
- Scarring, shift table by visit (observed cases): subjects enrolled in LP0084-1369
- Adverse events summary for LP0084-1369: subjects enrolled in LP0084-1369
- Adverse events summary (week 8 - months 14 in main trials and LP0084-1369): follow-up analysis set

Trial ID: LP0084-1369	Date: 27-May-2018	Version: 1.0 Page 12 of 14
-----------------------	-------------------	-------------------------------

- Adverse events by SOC and preferred term in LP0084-1369: subjects enrolled in LP0084-1369
- Adverse events by SOC and preferred term (week 8 - months 14 in main trials and LP0084-1369): follow-up analysis set
- Frequent adverse events ($\geq 2\%$ in the active treatment group) by SOC and preferred term in LP0084-1369: subjects enrolled in LP0084-1369
- Frequent adverse events ($\geq 2\%$ in the active treatment group) by SOC and preferred term (week 8 - months 14 in main trials and LP0084-1369): follow-up analysis set
- Adverse events by severity, SOC and preferred term in LP0084-1369: subjects enrolled in LP0084-1369
- Adverse events by severity, SOC and preferred term (week 8 - months 14 in main trials and LP0084-1369): follow-up analysis set
- Related adverse events by SOC and preferred term in LP0084-1369: subjects enrolled in LP0084-1369
- Related adverse events by SOC and preferred term (week 8 - months 14 in main trials and LP0084-1369): follow-up analysis set
- Related adverse events by severity, SOC and preferred term in LP0084-1369: subjects enrolled in LP0084-1369
- Related adverse events by severity, SOC and preferred term (week 8 - months 14 in main trials and LP0084-1369): follow-up analysis set
- Serious adverse events by SOC and preferred term in LP0084-1369: subjects enrolled in LP0084-1369
- Serious adverse events by SOC and preferred term (week 8 - months 14 in main trials and LP0084-1369): follow-up analysis set
- Serious adverse events by causal relationship, SOC and preferred term in LP0084-1369: subjects enrolled in LP0084-1369
- Serious adverse events by causal relationship, SOC and preferred term (week 8 - months 14 in main trials and LP0084-1369): follow-up analysis set

Trial ID: LP0084-1369	Date: 27-May-2018	Version: 1.0 Page 13 of 14
-----------------------	-------------------	-------------------------------

- SCC or other skin neoplasia inside treatment area by lowest level term in LP0084-1369: subjects enrolled in LP0084-1369
- SCC or other skin neoplasia inside treatment area by lowest level term (week 8 - months 14 in main trials and LP0084-1369): follow-up analysis set
- SCC or other skin neoplasia (consolidated terms) inside treatment area by preferred term in LP0084-1369: subjects enrolled in LP0084-1369
- SCC or other skin neoplasia (consolidated terms) inside treatment area by preferred term (week 8 - months 14 in main trials and LP0084-1369): follow-up analysis set
- Non-serious adverse events by SOC and preferred term in LP0084-1369: subjects enrolled in LP0084-1369
- Non-serious adverse events by SOC and preferred term (week 8 - months 14 in main trials and LP0084-1369): follow-up analysis set
- Adverse events leading to withdrawal by SOC and preferred term in LP0084-1369: subjects enrolled in LP0084-1369
- Adverse events leading to withdrawal by SOC and preferred term (week 8 - months 14 in main trials and LP0084-1369): follow-up analysis set

Figures

- Kaplan-Meier curve for SCC (face/chest): full analysis set
- Kaplan-Meier curve for SCC (landmark analysis, face/chest): follow-up analysis set
- Kaplan-Meier curve for SCC (scalp): full analysis set
- Kaplan-Meier curve for SCC (landmark analysis, scalp): follow-up analysis set
- Kaplan-Meier curve for SCC: full analysis set
- Kaplan-Meier curve for SCC (landmark analysis): follow-up analysis set
- Kaplan-Meier curve for SCC or other skin neoplasia (face/chest): full analysis set
- Kaplan-Meier curve for SCC or other skin neoplasia (landmark analysis, face/chest): follow-up analysis set
- Kaplan-Meier curve for SCC or other skin neoplasia (scalp): full analysis set
- Kaplan-Meier curve for SCC or other skin neoplasia (landmark analysis, scalp): full analysis set

Trial ID: LP0084-1369	Date: 27-May-2018	Version: 1.0 Page 14 of 14
------------------------------	--------------------------	-------------------------------

- Kaplan-Meier curve for SCC or other skin neoplasia: full analysis set
- Kaplan-Meier curve for SCC or other skin neoplasia (landmark analysis): follow-up analysis set
- Onset of each SCC for face/chest (left panel) and scalp (right panel): follow-up analysis set
- Onset of each SCC or other skin neoplasia for face/chest (left panel) and scalp (right panel): follow-up analysis set

Listings

- Serious adverse events (week 8 - months 14 in main trials and LP0084-1369): follow-up analysis set

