11.1 Sample Size

No formal sample size calculation has been made. The sample size is determined by the number of subjects who complete Visit 11 in the pivotal phase 3 trials (LP0084-1193, -1194, -1195, -1196) and are willing to enter the extension protocol. Two thirds have been treated with ingenol disoxate, one third with vehicle.

A total of 1200 subjects were planned be enrolled in the pivotal phase 3 trials (LP0084-1193, -1194, -1195, and -1196) and randomised 2:1 to the two treatment groups ingenol disoxate gel or vehicle gel. With 800 subjects in the ingenol disoxate treatment group and 400 subjects in the vehicle gel group, an adequate precision of the 3-year plus 2 months incidence rate can be obtained. Assuming a 3-year plus 2 months rate of 4.0%, the upper 95% confidence limit will on average be 5.36% for ingenol disoxate gel and 5.92% for vehicle gel, and assuming a 6.0% rate, the upper 95% confidence limit will on average be 7.65% for ingenol disoxate gel and 8.33% for vehicle gel.

Trial ID: LP0084-1369	Date: 25-Jul-2017	Version: 2.0 Page 24 of 52
-----------------------	-------------------	-------------------------------

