6.1 Subjects enrolled in to LP0084-1369

A total of 562 subjects consented to and were enrolled into the extension trial LP0084-1369.

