6.2 Full Analysis Set

A total of 1243 subjects were randomized in the 4 main trials. A total of 9 subjects withdrew consent prior to first application of investigational medicinal product (IMP). IMP was handed out to all 9 subjects but they returned the IMP unused. For all 9 subjects the decision to withdraw could therefore not have been biased by knowledge of the assigned treatment. The 9 subjects were excluded from the full analysis set (FAS) in alignment with ICH E9.

The remaining 1234 randomized subjects applied IMP and were included in the FAS.

Trial ID: LP0084-1369	Date: 27-May-2018	Version: 1.0 Page 7 of 14
-----------------------	-------------------	------------------------------

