6.4 Follow-up Analysis Set

The follow-up analysis set (FUAS) was defined as subjects in the FAS who were still in one of the main trials at visit 7 (week 8) and/or for whom evaluations after visit 7 (week 8) were available. The FUAS consists of 1172 subjects.

A difference between actual and planned treatment was only observed for 1 subject in FAS. The planned treatment was vehicle but the subject was treated with Ingenol Disoxate. The subject was included in FUAS but did not experience an event of SCC or other skin neoplasia.

7 Statistical Analysis

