7.3 Analysis of Safety

7.3.1 Adverse Events

AEs will be analysed as described in the CTP. AE tables will show the number of subjects and events. When counting the number of events multiple occurrences of the same preferred term within a subject will be counted as multiple events. Due to the premature stop of the trial no statistical testing will be performed for AEs. The CTP specified that serious adverse events (SAEs) occurring outside the treatment areas and considered not related to IMP in the main trials, should not be collected. Sporadically reported SAEs outside treatment area will therefore be removed from the ADaM datasets, but will appear in the SDTM datasets and the listing.

AEs that were ongoing at the end of the main trials were re-entered in the LP0084-1369 database for subjects enrolled in LP0084-1369, and these events were marked in the SDTM domain SUPPAE as such. A total of 69 AEs were re-entered in the LP0084-1369 database. The corresponding AEs in the main trials were identified by merging by subject, reported term and start date. In the 4 cases where the AEs in the main trials could not be identified by merging a manual review was performed to identify the corresponding AEs in the main trials. In cases of duplicate AEs only the AEs recorded in LP0084-1369 were included in the ADaM dataset. The analyses of AEs will be based on the actual treatment.

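### The pooled AE tables report crude percentages over 1172 subjects of whom at most 562 have extension follow-up, so the percentages refer to no defined period and are sensitive to unequal uptake by arm

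*SAP*

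**What the plan says.** **Tables.** SAP Appendix I lists AE tables that join the main-trial period from Week 8 to Month 14 with the extension. The first is "Adverse events summary (week 8 - months 14 in main trials and LP0084-1369): follow-up analysis set". The same pooled form is planned for tables by system organ class and preferred term, frequent events (at least 2% in the active group), severity, related, serious, non-serious and withdrawal events, and skin neoplasia by term.

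**Statistic.** SAP 7.3.1 follows the protocol and adds that "AE tables will show the number of subjects and events". Protocol 11.3.6.1 asks for the number and percentage of subjects by main-trial treatment group. Neither document plans person-time, censoring or a rate for AEs. SAP 7.3.1 also drops the AE tests.

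**Denominator.** SAP 6.4 states "The FUAS consists of 1172 subjects". Membership depends on being "still in one of the main trials at visit 7 (week 8) and/or for whom evaluations after visit 7 (week 8) were available", not on entering the extension.

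**Extension.** SAP 6.1 states "A total of 562 subjects consented to and were enrolled into the extension trial LP0084-1369". Entry was voluntary (Protocol 6.3), and SAP section 5 reports that the sponsor stopped the trial early.

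**Contrast.** For squamous cell carcinoma (SCC) and other skin neoplasia, SAP 7.2.1 divides by total observation time, and SAP 7.4.1 censors those who did not join the extension when they complete the main trial.

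**The concern.** A subject who left after Month 14 and a subject followed well into the extension each count as one in the denominator. Even with perfectly balanced arms, the result is a mixture of a roughly 12-month risk and a longer one, with weights set by uptake. It cannot be quoted as the risk over any stated period. The 2% cut-off for frequent events is applied to the same mixed figure.

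The comparison between arms is a separate matter. It is distorted only if uptake or extension length differs by arm. The documents contain routes by which that could happen. Entry was a later, voluntary choice. Subjects needing ingenol treatment in the area were excluded (Protocol 7.3), and those who used it had to be withdrawn (Protocol 7.7). Blinding was not maintained in the extension (Protocol 6.5). With no AE tests planned, readers will compare the percentages by eye.

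**Working it through.** **Inputs from the documents**

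- Randomised: "A total of 1243 subjects were randomized in the 4 main trials" (SAP 6.2). Nine were excluded, and 1243 − 9 = 1234 agrees with "The remaining 1234 randomized subjects applied IMP and were included in the FAS".
- Follow-up analysis set 1172 (SAP 6.4); enrolled in the extension 562 (SAP 6.1).
- Allocation: "Two thirds have been treated with ingenol disoxate, one third with vehicle" (Protocol 11.1).
- Main-trial period from Week 8 to Month 14: about 1 year.

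The documents give no planned figure for these AE tables to reproduce.

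**Share with extension follow-up**

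562 / 1172 = 48.0%, and 1172 − 562 = 610 subjects (52.0%) contribute no extension time. The 48.0% is an upper bound on those assessed after Month 14, because it counts enrolment and the trial stopped early.

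**Effect of unequal uptake (illustration)**

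Assumptions, none of them document figures: the same constant first-event rate L per year in both arms; 1 year of main-trial follow-up for everyone; d further years for the fraction u who enter the extension.

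Crude risk = (1 − u)(1 − exp(−L)) + u(1 − exp(−L(1 + d)))

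Worked case, L = 0.05 and d = 1: 1 − exp(−0.05) = 0.04877 and 1 − exp(−0.10) = 0.09516.

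- Active, u = 0.50: 0.50 × 0.04877 + 0.50 × 0.09516 = 7.20%
- Vehicle, u = 0.36: 0.64 × 0.04877 + 0.36 × 0.09516 = 6.55%
- Ratio 1.10, difference 0.65 points, although the true rates are equal.

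| Uptake, active / vehicle | d (years) | L | Crude risk, active / vehicle | Difference (points) | Ratio |
|---|---|---|---|---|---|
| 50% / 36% | 0.5 | 0.05 | 6.05% / 5.72% | 0.33 | 1.06 |
| 50% / 36% | 0.5 | 0.10 | 11.72% / 11.10% | 0.62 | 1.06 |
| 50% / 36% | 1 | 0.05 | 7.20% / 6.55% | 0.65 | 1.10 |
| 50% / 36% | 1 | 0.10 | 13.82% / 12.62% | 1.21 | 1.10 |
| 48% / 48% | any | any | equal | 0.00 | 1.00 |

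The ratio tracks mean follow-up: (1 + 0.50 × 0.5) / (1 + 0.36 × 0.5) = 1.25 / 1.18 = 1.06, and 1.50 / 1.36 = 1.10. A difference in duration would act in the same way.

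At 2:1 allocation, 50% and 36% average (2 × 50 + 36) / 3 = 45.3%, a little under the 48.0% enrolled. Keeping the same kind of gap but matching 562 of 1172 (53% versus 38%) gives the same ratios to two decimals, 1.06 and 1.10.

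**Smaller gaps**

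With uptake of 51.3% versus 41.3%, a 12-month risk of 20% and a 12-month extension, the crude figures are 28.2% and 26.6% (+1.6 points). With a 3-month extension the gap falls to +0.4 points. Across uptake gaps of 5 to 15 points, extensions of 3 to 12 months and 12-month risks of 5% to 20%, the spurious difference runs from about 0.1 to 2.4 points.

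**The case against.** **No arm imbalance is shown.** A reader might infer that the pooled AE comparison is biased because only 48% entered the extension. The documents do not support that. Low uptake alone leaves the comparison unbiased, the early stop applied to the whole trial, and uptake by arm is not given. This stands, and it limits the point to a sensitivity.

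**Large distortions do not fit the dates.** A reader might assume two extension years per entrant, which would put the 50% versus 36% ratio near 1.16. The planned first visit was Q2 2017 (Protocol 6.2), and the SAP of 27 May 2018 already reports the stop. AE collection runs from Visit 11, which can precede entry by about 6 months. On the planned dates even the earliest entrant could have only about 20 months by then, so a 2-year average is not possible. This stands; hence the 0.5 to 1 year range.

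**Much is already covered.** Appendix I gives extension-only AE tables on the enrolled subjects. Protocol 11.3.6.1 frames its AE summary on the 24-month period, so those tables serve the protocol's AE evaluation and the pooled ones are additional. Disposition is tabulated for both the full analysis set and the enrolled subjects, which should expose an imbalance in uptake. It would also be wrong to carry this point over to the SCC and neoplasia time-to-event analyses, which use censoring and person-time. All this stands as partial mitigation. What is still missing is a standalone Week 8 to Month 14 column and any AE person-time.

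**A pooled rate is not a clean remedy.** It assumes a constant hazard and like collection of events. The extension collects AEs only in the treatment area, with limited exceptions for serious events (Protocol 9.1), and counts local skin responses as AEs (Protocol 9.1.1). The documents do not give the main trials' AE rules for Week 8 to Month 14. This stands, and it is why separating the periods should come before any pooled rate.

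**Conclusion.** The point holds as a minor weakness of presentation. That the pooled percentages mix follow-up lengths and correspond to no defined period follows directly from the SAP's own counts (562 of 1172, 48.0%) and needs no assumption.

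Distortion between arms is conditional. It needs uptake or duration to differ by arm, and the documents are silent on both. Under the assumed 50% versus 36% uptake and 0.5 to 1 extension year, equal true rates appear as a ratio of about 1.06 to 1.10, or 0.3 to 1.2 points at rates of 0.05 to 0.10 per year. With the gap reversed the distortion runs the other way, and with equal uptake and duration it is nil. These figures also rest on a constant hazard and a full year of main-trial follow-up for everyone, which membership of the follow-up set does not guarantee.

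**What to change.** In SAP 7.3.1 and Appendix I:

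1. In each pooled AE table, show Week 8 to Month 14 (follow-up analysis set) as its own column beside the extension-only results already planned for the enrolled subjects.
2. State person-years by arm, and by location, for each period.
3. Add, for each period, subjects with events and events per 100 patient-years. For the first, stop a subject's time at the first event of that type; for the second, use all observed time.
4. Label any figure pooled across the two periods as secondary, and note that it assumes a constant hazard and the same AE collection rules.
5. Assign events to periods by start date, not by source database. SAP 7.3.1 keeps only the extension record where an ongoing event was re-entered (69 re-entered events), so a split by database would move earlier events into the extension.

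The cost is some programming and larger tables. Observation time is already needed for SAP 7.2.1. No data collection, hypothesis or primary analysis changes.
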